The primary outcome variables for this pilot trial are the Matsuda Whole-Body Composite Insulin Sensitivity Index (ISI) following an oral glucose tolerance test (OGTT), and the digital pulse volume response to arterial occlusion (blood pressure cuff) measured by reactive hyperemia peripheral tonometry (EndoPAT 2000, Itamar Medical, Caesarea, Israel). $ISI = 10\,000 / \sqrt{(\text{glucose}_{\text{fasting}} \times \text{insulin}_{\text{fasting}}) (\text{glucose}_{\text{mean}} \times \text{insulin}_{\text{mean}})}$ is strongly associated with the glucose-clamp procedure which is considered the gold standard for measuring insulin sensitivity^{50,51}. The EndoPAT 2000 has good reproducibility (ICC=0.74) and has been validated as a measure of endothelial function

with an 82% sensitivity and 77% specificity to diagnose coronary endothelial dysfunction⁵².

C4 Confirmation of Patient Eligibility

Confirm patient eligibility by collecting the information listed below:

1. Registering MD's name
2. Patient's race, BMI and DOB
3. Three letters (or two letters and a dash) for the patient's initials
4. Copy of signed consent form
5. Completed eligibility checklist, signed and dated by a member of the study team
6. Copy of appropriate source documentation confirming patient eligibility

C5 Assignment of UPN

Each patient will be identified with a unique patient number (UPN) for this study. All data will be recorded with this identification number on the appropriate CRFs.

Study Design

C6 Overview or Design Summary

The overall study design is a quasi-randomized, observational, 3-condition comparison of the acute effects of rest, resistance exercise or aerobic exercise on glucose metabolism and vascular function in obese women (n=15) during mid pregnancy.

C7 Subject Selection and Withdrawal

7.a Inclusion Criteria

1. First trimester BMI ≥ 30.0 and <45.0 kg/m² (calculated from clinical weight and height)
2. Singleton gestation, between 23 weeks and 0/7 days and 28 weeks and 0/7 days
3. Normal fetal anatomy (no major structural abnormalities identified on standard of care survey before enrollment)
4. Established prenatal care at Women's Health Clinic before 18 weeks of gestation, plans to deliver at Barnes-Jewish Hospital
5. Permission from Obstetrics physician provider to participate in study.

7.b Exclusion Criteria

1. Gestational or pre-gestational diabetes diagnosis
2. Inability to provide voluntary consent

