Assessment of Laboratory Clinical Variables: Venous blood will be collected from the participants to assess 1) CBC, 2) HbA1C, 3) complete metabolic panel, and blood hormone/metabolites including plasma glucose, insulin, c-peptide, free fatty acid, placental growth factor and vascular endothelial growth factor (VEGF).

The participant will quietly lie in bed for 45 minutes.

Immediately following the 45-minute rest period:

Assessment of Laboratory Clinical Variables: Venous blood will be collected from the participants to assess 1) CBC, 2) HbA1C, 3) complete metabolic panel, and blood hormone/metabolites including plasma glucose, insulin, c-peptide, free fatty acid, placental growth factor and vascular endothelial growth factor (VEGF).

Assessment of Vascular Function

Endothelial Function: Reactive hyperemia peripheral tonometry (RHPT, EndoPAT2000, Itamar Medical, Caesarea, Israel) will be measured before, and immediately post-exercise to assess digital pulse volume responses to arterial occlusion (blood pressure cuff). Briefly, the participant is placed in a sitting position and two disposable, inflatable probes are placed on the index fingers. Following 10 min of baseline signal recording, a blood pressure cuff is inflated for 3-min and following release, the hyperemic response is recorded for 5-min. The EndoPAT 2000 has good reproducibility (ICC=0.74) and has been validated as a measure of endothelial function with an 82% sensitivity and 77% specificity to diagnose coronary endothelial dysfunction⁵².

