Large Artery Function: Central aortic blood pressure and pressure waveforms. Pressure waves will be recorded sequentially from different sites, and transit time calculated using registration with a simultaneously recorded ECG by use of the SphygmoCor™ system (AtCor, Sydney, Australia), which has been well-validated and is approved by the FDA for the noninvasive assessment of central blood pressures and central aortic compliance by measurement of pulse wave velocity (PWV) and augmentation index (AIx). In this system, a single high-fidelity applanation tonometer (Millar) is used to obtain a proximal (i.e. carotid artery) and distal pulse (i.e. radial or femoral) recorded sequentially a short time apart; from this, the PWV is calculated from the transit time between the two arterial sites, determined in relation to the R-wave of the ECG. The time between the ECG and the proximal pulse is subtracted from the time between ECG and distal pulse to obtain the pulse transit time. In the case of stiff arteries, PWV rises and the reflected wave arrives back at the central arteries earlier, adding to the forward wave and augmenting the systolic pressure. This phenomenon can be quantified through the augmentation index (AIx), which is defined as the difference between the second and first systolic peaks (P2-P1) expressed as a percentage of the pulse pressure

Central hemodynamics and aortic compliance will be characterized using the SphygmoCor™ system. Pressure waves will be recorded sequentially from different sites using the SphygmoCor™ system (AtCor) using methods described by our group.⁵³ Derived indices include the central blood pressures and central aortic compliance characterized as the augmentation index (AIx) and pulse-wave velocity (PWV).

At 60-minutes following the end of the rest period:

Assessment of Glucose Metabolism

Two-hour oral glucose tolerance test (OGTT): At 60-min following the end of the rest period, a 2-hr oral OGTT will be conducted. Venous samples for glucose, insulin, and C-peptide will be drawn at time 0 and then 30, 60, 90 and 120 minutes after starting

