ingestion of glucola (1.75 g/kg of body weight to a maximum of 75 g). Insulin sensitivity and insulin secretion will be estimated by the Matsuda Whole-Body Composite Insulin Sensitivity Index (ISI), HOMA-IR, Insulinogenic Index and C-peptide Index. $ISI = 10\,000 / \sqrt{(\text{glucose}_{\text{fasting}} \times \text{insulin}_{\text{fasting}}) (\text{glucose}_{\text{mean}} \times \text{insulin}_{\text{mean}})}$, $HOMA-IR = (\text{Insulin}_{t0} \text{ mU/L} \times \text{Glucose}_{t0} \text{ mmol/L}) / 22.5$, Insulinogenic Index ($\Delta I_{30} / \Delta G_{30}$) and C-peptide index ($\Delta C\text{-peptide}_{30} / \Delta G_{30}$) will be calculated as previously described⁵⁴⁻⁵⁶. Area under the curve for glucose, C-peptide and insulin levels will also be calculated by trapezoidal integration over the entire OGTT for glucose tolerance assessment.

Lunch will be provided.

At 30-minutes following lunch:

Peak Exercise Testing ($VO_{2\text{peak}}$)

Participants will perform a graded exercise test on a recumbent cycle ergometer located on the WUSM CTRU. Continuous ECG/BP and oxygen consumption (VO_2) will be recorded during the graded exercise test to determine peak exercise capacity ($VO_{2\text{peak}}$). The graded exercise test protocol consists of 1-min incremental stages, beginning with a 20-watt workload, progressing every minute by 10-20-watts until volitional exhaustion or symptom limitation. Exercise tests will be considered maximal if peak heart rate $\geq 85\%$ predicted maximum (220-age) and/or respiratory exchange ratio ≥ 1.1 according to the American College of Sports Medicine⁵⁷. Peak exercise testing will be supervised by a licensed physical therapist and the CTRU nursing staff.

Ten-Repetition Maximum Strength testing (10RM)

10RM will be determined on 4-upper body and 4-lower body exercises on Universal exercise machines (Body Master®) located on the WUSM CTRU. 10-RM is the maximum amount of weight a participant can lift 10 times using proper form and only primary muscle groups required for the lifting motion. 10RM will be determined on each exercise device by trial and error.

D3 Visit 2

The evening before the study visit #2, participants will consume a standardized meal consisting of 55% carbohydrate, 30% fat, and 15% protein provided by the WUSM Bio-Nutrition Facility. The following morning, fasted participants (10 hrs) will be admitted to the WUSM CTRU at 7:00 am. Maternal weight (calibrated scale) and height (stadiometer) will be measured.

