Acute Aerobic Exercise or Resistance Exercise Session

Visit # 2 will consist of either: A) a 45-minute aerobic exercise (AE) session on a recumbent cycle ergometer at 70% $VO_{2\text{peak}}$, or B): a 45-minute resistance exercise (RE) session. The RE session will consist of 3 sets of 8-10 repetitions at their 10RM load according to the Adult NIH Molecular Transducers of Physical Activity in Humans (MoTrPAC) Study Protocol: <https://www.motrpac.org/protocols.cfm>. The acute RE session will be individualized, based on the measurements taken from a 10RM (measured without Valsalva maneuver) tests during Visit #1 for 1) knee extension, 2) knee flexion, 3) leg press (i.e. hip and knee extension), 4) ankle plantar flexion, 5) chest press, 6) seated row, 7) bicep curl (elbow flexion), and 8) overhead press. For each exercise, 3 sets of 8-10 repetitions will be performed with a 2-minute rest in between

sets. A 3-second contraction duration for the concentric and a 3-second contraction duration for the eccentric phase of the lift will be targeted. Fasting blood samples will be taken at pre-AE/RE/rest, at 20-min during AE/RE, immediately post-AE/RE/rest, and 60-min post AE/RE/rest as per MoTrPAC protocol. All visits will be separated by 1 week and rest, AE and RE visit order will be randomized through a computerized randomization program. The study scheme is presented in the Figure.

Assessment of Glucose Metabolism

At 60-min following the completion of AE/RE, a 2-hr oral OGTT will be conducted as described in Visit 1.

Assessment of Vascular Function

Endothelial and large artery function testing will be performed as described in Visit 1.

D3 Visit 3

The evening before the study visit #3, participants will consume a standardized meal consisting of 55% carbohydrate, 30% fat, and 15% protein provided by the WUSM Bio-Nutrition Facility. The following morning, fasted participants (10 hrs) will be admitted to the WUSM CTRU at 7:00 am. Maternal weight (calibrated scale) and height (stadiometer) will be measured.

Acute Aerobic Exercise or Resistance Exercise Session

Visit # 3 will consist of either: A) a 40-minute aerobic exercise (AE) session on a recumbent cycle ergometer at 70% VO_{2peak} , or B): a 40-minute resistance exercise (RE) session as described above.

Assessment of Glucose Metabolism

At 60-min following the completion of AE/RE, a 2-hr oral OGTT will be conducted as described in Visit 1.

Assessment of Vascular Function

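### The plan says the order of rest, AE and RE is randomized, but the visit schedule fixes rest at Visit 1, so exercise versus rest is a fixed-order, non-randomized contrast and F2 does not say so

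*Combined protocol and SAP*

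**What the plan says.** **Randomization.** D3 Visit 2 says that "rest, AE and RE visit order will be randomized through a computerized randomization program". C6 labels the study a "quasi-randomized, observational, 3-condition comparison" without saying which element is not randomized.

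**Schedule.**
- Visit 1 (D2) is the rest session: "The participant will quietly lie in bed for 45 minutes". The glucose test is timed from it: "At 60-min following the end of the rest period, a 2-hr oral OGTT will be conducted". No exercise alternative is offered.
- Later on the same day come the VO2peak test ("Participants will perform a graded exercise test on a recumbent cycle ergometer located on the WUSM CTRU") and the 10RM strength test.
- D3 Visit 2: "Visit # 2 will consist of either: A) a 45-minute aerobic exercise (AE) session", or an RE session. Rest is not an option.
- D3 Visit 3: "Visit # 3 will consist of either: A) a 40-minute aerobic exercise (AE) session", or an RE session. Rest is again not an option.
- AE is set at 70% of VO2peak. The RE session is individualized, "based on the measurements taken from a 10RM (measured without Valsalva maneuver) tests during Visit #1".

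**Analysis.** F2 plans a repeated measures ANOVA across three conditions with post-hoc tests. It expects to detect AE/RE versus rest and doubts that it has power for AE versus RE. Its parenthetical list of conditions has the word acute where rest should stand, although the next sentence does name rest as the comparator. F2 has no visit, order or gestational-age term, and no remark that rest always comes first.

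**The concern.** The contrast F2 expects to detect is the one the schedule does not randomize. If rest is always first, exercise versus rest is also later visit versus first visit. A shift in insulin sensitivity or endothelial response over that interval, familiarity with the procedures, or a difference in visit conditions would be counted as an exercise effect or would hide one.

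The randomization sentence invites readers of a publication, and planners of the larger multisite trial, to treat the estimate as protected against this. It is not, and enrolling more women would not change that. AE versus RE, the contrast the schedule does allow to be randomized, is the one F2 regards as underpowered.

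**Working it through.** **The plan's own figures.** F1 gives n=14 (glucose metabolism) and n=11 (vascular function). Neither can be reproduced, because F1 states no significance level, power or standard deviation. The point here does not depend on them.

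**1. Possible orders.** Three conditions have 3! = 6 orders. With rest at Visit 1 and AE or RE at Visits 2 and 3, two remain: rest-AE-RE and rest-RE-AE. The dependence is structural, since the exercise loads need the VO2peak and 10RM results from Visit 1.

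**2. Estimability.** Inputs: 15 women (C6), three visits each, 45 observations. An 8:7 split between the two orders is assumed, as the documents do not state one. Variances are in units of the residual variance.

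| Model and orders | Columns | Rank | AE - rest | RE - rest | AE - RE |
|---|---|---|---|---|---|
| Subject + condition, two orders | 15 + 2 = 17 | 17 | 0.1333 | 0.1333 | 0.1333 |
| Subject + condition + visit factor, two orders | 17 + 2 = 19 | 18 | not estimable | not estimable | 0.1339 |
| Subject + condition + visit factor, all six orders | 19 | 19 | 0.1339 | 0.1357 | 0.1339 |
| Subject + condition + linear time, two orders, weekly visits | 17 + 1 = 18 | 18 | 0.4214 | 0.4482 | 0.1339 |

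The first row is 2/15 = 0.1333. In the second row, the indicator for not being at rest equals the indicator for not being at Visit 1, so the two cannot be separated. Adding visit to the ANOVA therefore does not rescue exercise versus rest under this schedule. The third row shows that the cause is the fixed position of rest, not the number of women.

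**3. What enters the contrast.** Let d2 and d3 be the changes from Visit 1 to Visits 2 and 3 that would occur without exercise. Without a visit term and with the 8:7 split:
- AE - rest is off by (8·d2 + 7·d3)/15
- RE - rest is off by (7·d2 + 8·d3)/15
- their average is off by (15·d2 + 15·d3)/30 = (d2 + d3)/2
- AE - RE is off by (d2 - d3)/15

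The third expression does not contain n. The fourth is small because order is nearly balanced.

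**4. Which outcomes.** The Matsuda index comes from one glucose test per visit, so its exercise-versus-rest comparison is necessarily between visits. For EndoPAT, D2 describes readings before and immediately after exercise. If the post-session values are compared between conditions, step 3 applies. If the within-visit change is analysed, any shift that affects both readings of a visit equally cancels. F2 does not say which is meant. D2 also leaves unclear whether a pre-rest reading is taken at Visit 1, because the vascular assessment is listed after the rest period.

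**5. Related visit details.**
- Admission is at 8:00 am in D2 and at 7:00 am in D3 Visits 2 and 3.
- Sessions last 45 minutes at Visit 2 and 40 minutes at Visit 3. With the 8:7 split, mean AE length is (8×45 + 7×40)/15 = 42.7 minutes and mean RE length is (8×40 + 7×45)/15 = 42.3 minutes, so the effect on AE versus RE is small if order is balanced.
- Visit spacing is at least 4 days in D2 and 1 week in D3 Visit 2.

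**The case against.** **The design is already disclosed.** C6 calls the study quasi-randomized and observational, and the visit text openly puts rest first. This stands in part: disclosure is incomplete, not absent. But C6 does not identify the fixed element, the D3 sentence still claims all three conditions, and F2 is silent.

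**F1 does not power exercise versus rest.** A reader might infer from F2 that the sample size was built on that contrast. The documents do not support this. F1 speaks of independent acute effects of AE and RE, never names rest, and bases its vascular n=11 on pre/post change. That objection stands. The point concerns the between-condition comparison in F2.

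**Gestational age is not perfectly confounded with exercise.** A reader might infer that it is. The aliasing is with visit as a factor. With a linear time term the exercise contrasts are estimable, at about 3.2 and 3.4 times the variance (0.4214/0.1333 and 0.4482/0.1333), and only if the drift really is linear.

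**Some of the visit details may not be real conflicts.** A 1-week gap satisfies a 4-day minimum. The D2 paragraph giving 8:00 am opens by referring to all three visits, so it may simply contradict D3 and not be a Visit 1 feature. Both observations are fair. They reduce these items to matters for reconciliation.

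**This is a pilot with 15 women.** True, but F1 anticipates enough power for a publication, and the results are to inform a larger trial.

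**Conclusion.** The randomization statement contradicts the schedule. Under the schedule as written, 2 of 6 orders are possible and only AE versus RE can be a randomized comparison. Exercise versus rest is fixed-order. With a visit factor it is not estimable (rank 18 of 19 at n=15). Without one it carries (d2 + d3)/2 at any sample size. The rank result rests only on the visit descriptions; the variances and the small AE-RE term assume an 8:7 split.

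The finding covers the Matsuda index, and EndoPAT if post-session values are compared between conditions. It applies less to within-visit EndoPAT change.

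A reader might go further and infer that an observed benefit would be spurious, or that the false-positive rate is inflated by a known amount. The documents support neither. B1 says only that low insulin sensitivity is exaggerated in pregnancy. It gives no rate over the weeks concerned, so drift could mimic an exercise effect, mask one, or be negligible. The correction is needed because the plan misdescribes how its leading contrast is allocated, not because of any assumed drift.

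**What to change.** 1. **Randomization (D3 Visit 2 and C6).** Reconcile both with the visit schedule. If the schedule stands as written, state that rest is always the first visit and that only AE/RE order is randomized.
2. **Analysis (F2).** Correct the condition list to rest, AE and RE. Report exercise versus rest as a fixed-order, non-randomized contrast that includes any visit or gestational change, and AE versus RE as the randomized contrast. State whether EndoPAT is compared as a post-session value or as a within-visit change.
3. **Visit details (D2 and D3).** Reconcile the passages on admission time (8:00 versus 7:00 am) and session length (45 versus 40 minutes), and use one statement of visit spacing (at least 4 days, or 1 week).

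Cost: wording only. No extra women, samples or model degrees of freedom are needed. The downside is a more cautious claim about exercise versus rest.

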3. Currently using illegal drugs (e.g., cocaine, methamphetamine, opiates) (safety risk and potential confounding)
4. Current smoker who does not agree to stop (confounding)
5. Participation in routine (>1 x/week) exercise program (may improve glucose metabolism/vascular function)
6. History of heart disease, orthopedic, metabolic or neurological condition that would contraindicate exercise (safety risk)

Inclusion of Women and Minorities

Women and members of all races and ethnic groups are eligible for this trial. Men are not eligible.

7.c Subject Recruitment Plans and Consent Process

Participants will be recruited from the Center of Women's Health at Washington University School of Medicine/Barnes Jewish Hospital. All obese (BMI \geq 30) patients with on-going pregnancies will be approached for study participation at the first visit in the the trained clinical research coordinator. Patients will be approached through direct personal recruitment through the clinic and consented.

7.d Early Withdrawal of Subjects

Research participation will occur on three separate visits. Participants will be withdrawn if they are unable to complete the procedures during any of the research visits.

7.e Data Collection and Follow-up for Withdrawn Subjects

There will be no follow up of withdrawn participants.

D Study Procedures

D1 Screening for Eligibility

Pregnant women with obesity: Eligibility criteria of patients attending the Center of Women's Health at Washington University School of Medicine/Barnes Jewish Hospital will be reviewed by [name] and by the research coordinator.

D2 Visit 1

These procedures will be performed on over 3 visits separated by \geq 4 days. Participants will be studied within gestation weeks 23-30. The evening before the study visits, participants will consume a standardized meal consisting of 55% carbohydrate, 30% fat, and 15% protein provided by the WUSM Bio-Nutrition Facility. The following morning, fasted participants (10 hrs) will be admitted to the Clinical Translational Research Unit of the Institute of Clinical and Translational Sciences at Washington University School of Medicine (WUSM CTRU) at 8:00 am. Maternal weight (calibrated scale) and height (stadiometer) will be measured.

Body Composition Measurement: Whole-body fat will be quantified using through skin-fold anthropometry (Harpenden, West Sussex, UK).

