Attribution (relatedness), Expectedness, and Seriousness: the definitions for the terms listed that should be used are those provided by the Department of Health and Human Services' Office for Human Research Protections (OHRP). A copy of this guidance can be found on OHRP's website:

<http://www.hhs.gov/ohrp/policy/advevntguid.html>

1.b Serious Adverse Event (SAE)

Definition: any adverse drug experience occurring at any dose that results in any of the following outcomes:

- Death
- A life-threatening adverse drug experience
- Inpatient hospitalization or prolongation of existing hospitalization
- A persistent or significant disability/incapacity (i.e., a substantial disruption of a person's ability to conduct normal life functions)
- A congenital anomaly/birth defect
- Any other experience which, based upon appropriate medical judgment, may jeopardize the subject and may require medical or surgical intervention to prevent one of the outcomes listed above

1.c Unexpected Adverse Experience

Definition: any adverse drug experience, the specificity or severity of which is not consistent with the current investigator brochure (or risk information, if an IB is not required or available).

1.d Life-Threatening Adverse Experience

Definition: any adverse drug experience that places the subject (in the view of the investigator) at immediate risk of death from the reaction as it occurred, i.e., it does not include a reaction that, had it occurred in a more severe form, might have caused death.

1.e Unanticipated Problems

Definition:

- unexpected (in terms of nature, severity, or frequency) given (a) the research procedures that are described in the protocol-related documents, such as the IRB-approved research protocol and informed consent document; and (b) the characteristics of the subject population being studied;
- related or possibly related to participation in the research (“possibly related” means there is a reasonable possibility that the incident, experience, or outcome may have been caused by the procedures involved in the research); and
- suggests that the research places subjects or others at a greater risk of harm (including physical, psychological, economic, or social harm) than was previously known or recognized.

1.f Noncompliance

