Definition: failure to follow any applicable regulation or institutional policies that govern human subjects research or failure to follow the determinations of the IRB. Noncompliance may occur due to lack of knowledge or due to deliberate choice to ignore regulations, institutional policies, or determinations of the IRB.

1.g Serious Noncompliance

Definition: noncompliance that materially increases risks, that results in substantial harm to subjects or others, or that materially compromises the rights or welfare of participants.

1.h Protocol Exceptions

Definition: A planned deviation from the approved protocol that are under the research team's control. Exceptions apply only to a single participant or a singular situation.

Pre-approval of all protocol exceptions must be obtained prior to the event.

E2 Reporting to the Human Research Protection Office (HRPO) at Washington University

The PI is required to promptly notify the IRB of the following events:

- Any unanticipated problems involving risks to participants or others which occur at WU, any BJH or SLCH institution, or that impacts participants or the conduct of the study.
- Noncompliance with federal regulations or the requirements or determinations of the IRB.
- Receipt of new information that may impact the willingness of participants to participate or continue participation in the research study.

These events must be reported to the IRB within **10 working days** of the occurrence of the event or notification to the PI of the event. The death of a research participant that qualifies as a reportable event should be reported within **1 working day** of the occurrence of the event or notification to the PI of the event.

E3 Timeframe for Reporting Required Events

Adverse events will be tracked for 24 hours after date of participation. The event need not be causally related to 31P-MRS, blood draw, and echocardiogram to qualify as an adverse event to be collected.

F Statistical Plan

F1 Sample Size Determination and Power

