During monthly group meetings, the research team (Dr.'s [name], [name]) and the research coordinator will monitor and review: (a) Recruitment, screening and enrollment progress, goals and strategies; (b) Preliminary findings that might affect the risk/benefit ratio or alter the procedures described in the protocol; (c) Any out of range laboratory value and a course of action; (d) Any adverse or serious adverse events that might result from the research procedures. In monthly meetings, Drs. [name] and [name] will monitor and review: (a) research-related risks that might alter the risk/benefit ratio, (b) any laboratory or blood pressure findings that are out of range and require follow-up with the participant, (c) any new information/findings about obese pregnancy that might facilitate this study, reduce risk or the burden of testing for participants. All serious adverse events will be reported to the WUSM Human Research Protection Office (HRPO), NIH and the Research Subject Advocate on the WUSM Clinical Research Unit (CRU) within 15 days of the event. There are standard reporting forms for the WUSM CRU and the HRPO. Should there be a serious adverse event that increases the risks to participants, the study will be stopped, an investigation conducted, and findings generated before the study is resumed. These findings are shared with the HRPO, NIH and the Research Subject Advocate. If necessary, the research procedures are modified and appropriate revisions to the consent document and consent procedures are made. Each individual adverse event is reported to the WUSM HRPO which has the option of stopping or discontinuing this project if they deem that the risk/benefit ratio becomes too high. The HRPO may rule to continue the study once the research procedures are modified and appropriate revisions to the consent document and consent procedures are made. This Data Safety Monitor Committee plan is in compliance with and will be approved by The Research Advisory Committee of the CRU.

H Study Administration

H1 Organization and Participating Centers

Washington University is the only participating site.

H2 Funding Source and Conflicts of Interest

Departmental funding. No conflicts of interest.

H3 Subject Stipends or Payments

Participants will receive a total of \$150 for completion of the study.

I References

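### Adverse events are tracked for only 24 hours after each visit and nobody asks about the interval since the last one, so most of each between-visit gap is outside active collection

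*Combined protocol and SAP*

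**What the plan says.** Section E3 sets the collection window: "Adverse events will be tracked for 24 hours after date of participation". Its next sentence says that an event need not be caused by 31P-MRS, blood draw or echocardiogram to be collected. Of these three, only blood draw is a procedure in this study.

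Section 7.d describes participation: "Research participation will occur on three separate visits". Visit spacing is given twice. The Visit 2 section says "All visits will be separated by 1 week", while the Visit 1 section (D2) sets a minimum gap of 4 days.

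Visit 1 ends with a graded exercise test to exhaustion or symptom limitation and with ten-repetition maximum testing. The 70% VO2peak aerobic session and the resistance session are described under Visits 2 and 3. Those two sections cover the standardized meal, fasting admission, weight and height, the session, the OGTT and vascular testing. They contain no question about events since the last visit.

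Section 7.d withdraws a woman who cannot complete the procedures at any visit, and 7.e says that withdrawn women are not followed.

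Section E1 1.b counts inpatient hospitalization as serious. Section E2 requires prompt notice of unanticipated problems to the IRB. Section G requires all serious events to be reported within 15 days and adds: "Should there be a serious adverse event that increases the risks to participants, the study will be stopped".

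**The concern.** The window in E3 is much shorter than the gap between sessions. An event on the third or fourth day after exhaustive exercise testing falls outside it, and the plan then takes the woman into her next session without asking whether anything happened.

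Two things are at stake. First, a report of few or no adverse events would partly reflect when collection stopped. Second, the halt rule in Section G can act only on events that the team knows about. If nobody asks, it depends on the participant, her obstetric provider or the hospital raising the event unprompted.

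The withdrawal rule sharpens this. A woman who stops because of an event has no later study visit at which it could surface.

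**Working it through.** The 24-hour window is a design choice, so there is no plan figure to reproduce. The check is calendar arithmetic and a reading of the sections against each other.

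**Inputs**
- Window: 24 hours after the date of participation (E3), read as applying to each of the three visits (7.d).
- Gap between visits: 7 days (Visit 2 section) or at least 4 days (Visit 1 section, D2). A 7-day gap satisfies both statements; a 4-day gap satisfies only the second.
- Arrival times: 8:00 at Visit 1, 7:00 at Visits 2 and 3.

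**Share of each gap outside collection** = (gap − covered time) / gap

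| Reading of the 24 hours | Covered | 7-day gap | 4-day gap |
|---|---|---|---|
| One day from the visit | 1 day | (7 − 1)/7 = 6/7 = 86% | (4 − 1)/4 = 3/4 = 75% |
| Clock starts later, intermediate assumption | 1.5 days | 5.5/7 = 79% | 2.5/4 = 63% |
| Clock starts at midnight after a 7:00 arrival | 17 + 24 = 41 h | (168 − 41)/168 = 127/168 = 76% | (96 − 41)/96 = 55/96 = 57% |

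The second and third rows are assumptions about when the clock starts, because E3 does not say. The uncovered share runs from 57% to 86% across all readings.

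**From Visit 1 to 24 hours after Visit 3** (one day covered per visit)
- 7-day gaps: 2 × 7 + 1 = 15 days, of which 3 are covered (20%) and 12 are not.
- 4-day gaps: 2 × 4 + 1 = 9 days, of which 3 are covered (33%) and 6 are not.

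**Could another section find events in the uncovered days?**
- E2 sets clocks of 10 working days, or 1 working day for a reportable death, running from the event or from notice of it to the principal investigator. Section G sets 15 days from a serious event. These are reporting deadlines, not methods of detection.
- Section G reviews events at monthly meetings. Visit 1 to Visit 3 takes 14 days at weekly spacing (2 × 7) or 8 days at the minimum (2 × 4). A woman can finish before the next meeting, and the meeting can review only what was collected.
- No section describes contact or chart review between visits or after Visit 3.

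**Example.** A woman is admitted to hospital two days after a session. The admission is serious under 1.b. It falls at 48 hours, outside the E3 window on every reading above. It is reportable under Section G if known, but no step in the plan would make it known.

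**The case against.** The strongest reply is that E3 is not the only safety provision. The serious-event clause in Section G has no 24-hour limit, and E2 covers unanticipated problems at the university and its affiliated hospitals whenever they come to notice. Participants attend the recruiting clinic, need their obstetric provider's permission to join, and return for two more visits, so an important event may well be heard of. This stands in part: it would be wrong to say that the halt rule *would* miss a late admission. The supportable statement is that it *could*, because detection depends on notification.

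The size is also not one firm number. The spacing statements differ and the clock's start is undefined. That stands, but the gap is mostly uncovered on every reading.

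A reader might infer three stronger points that the documents do not support.

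- *That the plan names several pregnancy outcomes as serious and then fails to observe them.* The serious-event list has one pregnancy-specific item, "A congenital anomaly/birth defect", within a definition worded for drug trials. Stillbirth, preterm birth and preeclampsia appear only as background risks of obesity. Normal fetal anatomy is required at entry, which limits how many anomalies would first appear at birth.
- *That delivery records should be collected because entry requires that the woman "plans to deliver at Barnes-Jewish Hospital".* A plan to deliver there is not a delivery there. The aims concern acute effects, every woman is meant to receive all three conditions, and 15 uncontrolled births could not be attributed to any of them. Collecting these records would be a preference, not the repair of a defect.
- *That the pilot would carry no maternal safety information forward.* E3 collects events at each visit and for 24 hours afterwards, whatever their cause. That is limited information, not none.

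**Conclusion.** The concern holds for the days between visits. Active collection stops 24 hours after each visit, and the documents describe no interval question at Visits 2 and 3. About 6 of 7 days are uncovered at weekly spacing and 3 of 4 at the 4-day minimum. On the most generous reading of the clock these shares fall to 76% and 57%.

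The conclusion rests on reading the window as applying to each visit, and on the protocol text alone. Consent pages were not available, so any instruction there to report events cannot be judged. It does not extend to pregnancy outcomes after Visit 3.

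The 24 hours carries no stated rationale. Because E3 also names procedures from outside this study, the window may not have been chosen for this protocol. This is a cheap improvement to safety ascertainment. It does not affect the primary outcomes, the sample size or the analysis.

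**What to change.** - Amend E3 so that adverse events are collected continuously from the start of Visit 1 to a fixed point after Visit 3. The sponsor sets that point.
- Add to the Visit 2 and Visit 3 sections that events since the previous visit are asked about and recorded before any procedure begins.
- Reconcile this with 7.e, so that a woman who stops because of an event is still covered to the same end point.
- Replace the E3 reference to 31P-MRS and echocardiogram with this study's own procedures.
- Reconcile the two visit-spacing statements (1 week under Visit 2, at least 4 days under Visit 1).

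The cost is a protocol amendment, matching consent wording where needed, one scripted question at two existing visits, and a contact at the end point for up to 15 women, including any who withdrew. The downside is a few more unrelated pregnancy events to classify.
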